**Evaluating Public Health Interventions to Improve COVID-19 Testing Among
Underserved Populations**

PROTOCOL; STATISTICAL ANALYSIS; INFORMED CONSENT FORM

NCT05270694

07 November 2024

PROTOCOL

Using a community-based approach, we engaged participants from vulnerable communities in a cohort study focused on at-home COVID-19 testing. Participants received in-person instruction on testing and were provided with at-home COVID-19 test kits while answering monthly surveys on testing use and behavioral factors. By following a community engaged model we aimed to build trust and understanding in order to engage these vulnerable communities both effectively and ethically.

Setting and Participants

We conducted a longitudinal cohort study of at-home COVID-19 testing from March 2022 - November 2023, with recruitment focused on Portland, Maine. We aimed to engage a roughly equal number of participants from the immigrant, housing unstable, and low-income/uninsured communities. Individuals were eligible to participate if they were aged ≥ 18 years and either: 1) an immigrant; 2) currently unhoused or had a history of chronic homelessness; or 3) received services through Portland Public Health (specifically the Portland Community Free Clinic [PCFC], Sexually Transmitted Disease [STD] Clinic, or Needle Exchange). The MaineHealth Institutional Review Board approved the protocol.

Intervention

All participants attended an individual in-person enrollment session with research staff in which they were consented, learned to perform a COVID-19 test, completed a baseline survey, and received five at-home COVID-19 tests. Participants then received five at-home COVID-19 tests every eight weeks for 48 weeks (30 tests total), regardless of whether they used all previous tests; this constituted the “testing program.” Participants received their test kits either by mail or in-person at community partner sites or another location selected by the participant to ensure accessibility.

Measures

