The baseline survey included study-specific questions regarding COVID-19 test use and behavioral factors (i.e. risk perceptions, attitudes, norms), as well as the RADx-UP Common Data Elements (CDEs), a set of standardized questions used in National Institutes of Health (NIH) funded COVID-19 research to build a repository of COVID-19 data (details of the CDE are shown in Appendix A). Participants then completed a brief survey every four weeks on COVID-19 exposures, symptoms, and their use of COVID-19 tests. Every eight weeks participants completed a longer survey that included additional questions on behavioral factors around COVID-19 testing. The initial eight-week survey also included questions adapted from the validated National Institute on Drug Abuse (NIDA)-Modified ASSIST survey regarding substance use behaviors. In total, each participant completed one baseline and twelve follow-up surveys over the span of 11 months.

NIH translation services translated all recruitment and survey materials into seven languages (Somali, Arabic, French, Kinyarwanda, Lingala, Portuguese and Spanish) representing the top languages spoken by patients of GPH. We securely hosted and stored the surveys on a REDCap database, and distributed the REDCap survey link to participants over email, text, or WhatsApp. If requested, research staff also administered the surveys over the phone or in-person. Participants who did not respond to a survey were sent a reminder email/message up to three times over six days; on day seven they were called by research staff. Participants were considered lost to follow-up if they missed completing three consecutive surveys and could not be reached. Participants

could receive up to \$250 in grocery gift cards for their participation in the study: a \$50 gift card at enrollment, \$20 gift cards every eight weeks for completing surveys, and \$40 gift cards for reaching the half-way point and end of the study.

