The primary outcome was “desired testing behavior score.” In every survey, participants were asked whether, in the last month, they had a close contact exposure to a known case of COVID-19 or experienced symptoms concerning for COVID-19 (reporting yes/no to a list of twelve symptoms), indicating an instance where testing was CDC recommended. Following these questions, participants were then asked if, in the last month, they had taken a COVID-19 test. The “desired testing behavior score” was then calculated as the proportion of surveys in which a participant reported taking a COVID-19 test when they reported an indication to test. For example, if a participant reported a symptom and/or exposure in five of their surveys but only reported testing in three of those surveys, then their desired testing behavior score was 3/5, or 0.6.

Independent variables examined in the analysis included vulnerability groups, behavioral factors, and demographic variables. The four dichotomous vulnerability groupings included: 1) immigrants 2) unhoused or history of chronic homelessness 3) low-income and/or uninsured and 4) substance use. We also calculated a “vulnerability score” for each participant indicating the number of vulnerabilities each participant identified with. The five behavioral factor scores related to COVID-19 testing and illness, measured using 5-point Likert scale questions, were: 1) confidence in ability to use tests 2) perceived severity of illness from COVID-19 3) perceived usefulness of testing 4) norms around testing and 5) commitment to testing. Additionally, we analyzed seven demographic characteristics: age, sex, race, employment status, education level, COVID-19 vaccination status, and self-reported health status.

STATISTICAL ANALYSIS

We performed a descriptive analysis to characterize demographics and vulnerability status of the participants. We also stratified by vulnerability group to describe differences across groups. We examined whether COVID-19 testing behavioral factors differed by vulnerability group by using two-sample t-tests to perform difference testing between group and non-group for each behavioral factor score.

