We performed bivariate linear regressions to assess the association between desired testing behavior and each vulnerability, behavioral, and demographic factor. Factors significantly associated with desired testing behavior in the bivariate regressions were then included in a multivariate linear regression; the vulnerability score was also included, despite non-significance in bivariate analysis, as the previous literature and earlier qualitative analysis in our community indicated these categories have a strong relationship with testing. A linear relationship was confirmed by a plot of residuals against the predicted values. There was no evidence of multicollinearity, as assessed by tolerance values > 0.1 and VIF values < 10 . The assumption of normality was met, as assessed by visual inspection of the Q-Q plot. Analyses were conducted using STATA version 17.0.

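### The primary outcome is a per-person proportion with a varying denominator, but the linear regressions describe no robust standard errors and no constant-variance check, so some p-values may be wrong

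*Combined protocol and SAP*

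**What the plan says.** The Measures section defines the primary outcome, the desired testing behavior score, as "calculated as the proportion of surveys in which a participant reported taking a COVID-19 test when they reported an indication to test". Its worked example has five indicated surveys and three with a test, giving 3/5 = 0.6. The denominator is thus a personal count. Its ceiling comes from the survey schedule: "In total, each participant completed one baseline and twelve follow-up surveys over the span of 11 months". It can also fall through missed surveys, for which the plan has a rule: "Participants were considered lost to follow-up if they missed completing three consecutive surveys and could not be reached".

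The Statistical Analysis section analyses this score by linear regression: "We performed bivariate linear regressions to assess the association between desired testing behavior and each vulnerability, behavioral, and demographic factor". The results then drive model building: "Factors significantly associated with desired testing behavior in the bivariate regressions were then included in a multivariate linear regression". The vulnerability score is the one stated exception and enters regardless.

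Three assumption checks are reported. On linearity: "A linear relationship was confirmed by a plot of residuals against the predicted values". On normality: "The assumption of normality was met, as assessed by visual inspection of the Q-Q plot". The third is multicollinearity, by tolerance and VIF. Constant variance, robust standard errors, weighting by the denominator, and binomial or fractional models are not mentioned.

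**The concern.** A participant with one indicated survey can score only 0 or 1. A participant with thirteen has a score averaged over thirteen answers. Unequal variance therefore follows from the definition of the outcome, unless n hardly varies or a person's answers are almost perfectly correlated.

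This does not bias the coefficients. It does affect ordinary standard errors when n is related to the predictor and the groups are unequal in size. Both conditions are plausible. Self-reported health status is a predictor, and symptoms generate indications. Exposure and survey completion may differ by vulnerability group. The recruitment aim was "We aimed to engage a roughly equal number of participants from the immigrant, housing unstable, and low-income/uninsured communities", so a group-versus-rest split could lie near one third to two thirds. The documents contain no data showing that n does differ by predictor.

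These regressions supply every p-value for the primary outcome and decide which factors reach the multivariable model. If the smaller group has fewer indicated surveys, its intervals are too narrow and it may be selected falsely. If it has more, its intervals are too wide and a real factor may be dropped. Without the distribution of n, a reader cannot tell which applies.

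**Working it through.** **Inputs from the documents.** The outcome is k/n for each person. The maximum n is 1 + 12 = 13, or 12 if baseline is not counted. The plan states no sample size, power, significance level or standard deviation, so there is no design figure to reproduce. The example 3/5 = 0.6 is correct.

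**Assumed inputs.** Total sample N = 200 to 400, testing probability p = 0.6, within-person correlation (ICC) 0.1 to 0.4, two-sided 5% level.

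**Step 1: variance of one score.** Var = p(1−p)[ICC + (1−ICC)/n]. The ratio of the variance at n = 1 to that at n = 13 is 13/(1 + 12 × ICC):
- ICC 0.1: 13/2.2 = 5.9
- ICC 0.2: 13/3.4 = 3.8
- ICC 0.4: 13/5.8 = 2.2

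**Step 2: effect on the ordinary standard error.** Take a binary predictor whose subgroup is a share w of the sample, with score variance vA in the subgroup and vB in the rest. In large samples, the ordinary squared standard error divided by the true one is

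(w·vA + (1−w)·vB) / ((1−w)·vA + w·vB).

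This equals 1 if w = 0.5 or vA = vB, and otherwise it does not.

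Example: w = 0.33, n = 2 in the subgroup and 6 in the rest, ICC 0.1.
- vA = 0.24 × (0.1 + 0.9/2) = 0.132; vB = 0.24 × (0.1 + 0.9/6) = 0.060.
- Ratio = (0.0436 + 0.0402)/(0.0884 + 0.0198) = 0.774; its square root is 0.88, so the standard error is 12% too small.
- Type I error = 2Φ(−1.96 × 0.88) = about 8.5%.

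At ICC 0.4 the variances are 0.168 and 0.120, the square root is 0.945, and the type I error is 6.4%.

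**Step 3: simulation with n varying within groups.** Scores were beta-binomial with no true effect, 6,000 runs per setting. n was drawn from a beta-binomial on 13 surveys, truncated to at least 1. Ranges cover the assumed N and ICC.

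| Subgroup share | Mean n, subgroup vs rest | Type I error, ordinary errors |
|---|---|---|
| 33% | 4 vs 6 | 5.4-6.2% |
| 33% | 2 vs 6 | 6.5-9.1% |
| 20% | 4 vs 6 | 5.5-7.8% |
| 20% | 2 vs 6 | 7.5-12.3% |
| 33% | 6 vs 2 | 2.6-3.7% |
| 20% | 6 vs 2 | 1.5-2.9% |
| 50% | 2 vs 6 | 4.6-5.4% |
| any | n unrelated to predictor | 4.5-5.6% |

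HC3 errors gave 4.3-5.6% in every setting. For 33%, 2 vs 6 at N = 300, changing p to 0.4 or 0.8 gave 6.6-8.3% and 6.3-8.2%, so the result does not hinge on p = 0.6.

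**Step 4: wider assumptions.** A separate simulation used N = 150 and 300, ICC 0 to 0.5, shares of 15% to 85% and mean n up to 2 vs 8. Where n was related to the predictor and the groups were unequal, ordinary errors ranged from about 0.2% to 24%. HC3 stayed at about 4.4-6.1%. Results at the two sample sizes were similar, so a larger study does not remove the problem.

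**The case against.** The strongest reply is about size, and much of it stands.

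- **The harm is conditional.** It needs n to differ by predictor and the groups to be unequal, and the documents show neither. This is a possible fault, not a demonstrated one.
- **The larger figures sit badly with the reported Q-Q plot.** In a re-run of the 2 vs 6 settings at N = 300, 69-79% of the low-n group's scores, and 32-56% of all scores, were exactly 0 or 1. That is hard to reconcile with a Q-Q plot judged acceptable, although it was judged by eye. Real n may well be larger; 6 vs 8 at a one-third share gives only 5.1-6.1%.
- **Imbalance may be mild.** The thirds are recruitment targets, while the analysed groupings can overlap, which would tend to raise their shares. At a 45% share, 2 vs 6 gives 5.4-6.0%. No passage supports a 20% share.
- **A residual plot was made.** It could have shown unequal spread between the two fitted values of a binary predictor. But the text cites it for linearity alone, so no constant-variance check is on record.
- **The practical effect may be small.** With 4 groupings, 1 score, 5 behavioral and 7 demographic factors, 17 are screened. If all were null, expected false selections would rise from 17 × 0.05 = 0.85 to 17 × 0.06 = 1.02.
- **Only one binary predictor was simulated,** not the Likert scores or the multivariable model.

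None of this supplies the missing safeguard. Normality is not constant variance, and nothing reported lets a reader rule out the larger errors or their direction.

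**Conclusion.** The concern holds. Unequal variance is built into the primary outcome, and no step described in the plan deals with it. Ordinary p-values may be wrong for predictors related to the number of indicated surveys when groups differ in size.

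Under the stated assumptions the error runs from negligible (5.4-6.2% for a one-third subgroup at 4 vs 6) to moderate (6.5-9.1% at 2 vs 6). It is larger for smaller subgroups, and the test is conservative when the smaller group has the larger n. The reported Q-Q plot points towards the small end. There is no material error when groups are equal in size or n is unrelated to the predictor. Confidence is medium, because the sample size, shares, distribution of n and ICC are all assumed. It should be fixed, mainly because the same p-values select the final model and the remedy is cheap.

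**What to change.** Keep the per-person score. Re-run the bivariate and multivariable models with HC3 standard errors (in Stata 17, regress with vce(hc3)). Fractional logit with robust errors and average marginal differences is an acceptable alternative (fracreg logit with vce(robust), then margins). Repeat the factor selection with the new p-values.

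Report the distribution of n overall and by vulnerability group. Include how many participants had n = 0 and so no score; how they are handled is a separate gap.

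A survey-level logistic GEE or mixed model clustered by participant can be added as a sensitivity analysis. It can target an average over surveys rather than over persons. With ICC 0.2, mean n 5.3 and a latent correlation of +0.3 between n and testing propensity, the person average was 0.606 and the survey average 0.633; at −0.3 they were 0.594 and 0.567. Any gain in precision depends on the ICC.

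The cost is one sentence in the Statistical Analysis section and a short re-run of existing data. The downside is that some standard errors may widen and the set of selected factors may change.
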